
#### **14.2 Early Withdrawal of Subjects**

All participants may choose to withdraw from the study at any time. We will track date of discontinuation and request a brief reason to be recorded for tracking purposes. In the event of serious medical complications (or death) precluding participation, participants will be censored after 2 months of missing data. In all other cases, staff will continue to request surveys until 2 months following the study endpoint (12 months for RCT, 3 months for Run-In), as described above.

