In both arms of the study, if any participant declines to complete the full RPCA survey and/or if participants or family members report participants are unable to complete the survey due to illness complications, staff will offer in the following order: (a) an in-person (English-speaking, interview based) survey session, and (b) abbreviated versions of the questionnaire for patients to complete. Only at follow-up timepoints and in cases where participants are too ill to provide self report in writing or interviews, staff will offer abbreviated versions of the survey for *parents* to complete as proxy respondents. These options will be offered in an effort to collect full data for primary endpoint assessment, including the aRPCA or even a survey containing only the primary outcome of HRQOL.

Participants in both arms of the study will be scheduled for their surveys at the time of enrollment and then reminded prior to each survey due-date. Participants will be contacted by phone, email or mail to receive their RPCA survey. If we have not received a response within a day of initial contact, participants will receive up to 4 follow-up phone calls, texts, and/or emails (approximately once weekly) within a 28 day window before and after surveys are due. Participants will remain eligible for subsequent survey completion and follow-up even if surveys are missing and the same procedures will be conducted for each survey due-date until the 12-month follow-up point.

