#### **13.5 Data Collection Procedures/ Internal Site Monitoring plan**

The coordinating center will be responsible for systematic data collection, quality control, and data-management procedures including: (1) oversight of ongoing data collection; (2) rigorous training and ongoing monitoring of adherence to protocols; (3) regular review of questionnaire response rates and missing items to identify and correct problems; (4) verification of all data through computerized data entry systems restricting invalid/out-of-range responses; (5) at minimum monthly meetings and progress reports to provide feedback to study staff concerning difficulties and follow-up to ensure problems are resolved quickly; and, (6) yearly on-site monitoring of participating sites

**13.5.1 Survey data.** To optimize collection, all participant surveys will be available by paper or online via the REDCap system, a secure HIPAA-compliant, high-quality data collection tool. Surveys may also be completed in person with a study team member. The rationale for offering both paper-pencil and electronic versions is based on our prior experience where participants preferred the former, which in turn facilitated more complete data collection. To ensure primary outcome data, we will offer an interview and/or abbreviated survey with only the PedsQL for those who do not complete all assessments or who request to drop out or who are too ill to complete the entire survey. To ensure data quality, a RA will review RPCA surveys within 72 hours of their completion for missing fields and call participants sites to clarify and query/complete individual missing items verbally.

**13.5.2 Medical record data.** RA's will collect and upload CRF data monthly for both the run in and RCT 3 months post baseline. CRF data will also be collected at 6-, 9-, and 12-months for the RCT only. To ensure reliability and validity of abstracted medical record data, we will use our current methods for training and quality, including guided practice abstraction and independent abstraction with reconciliation by a trainer. A 10% random sample will be dual abstracted. A RA assignment will monitor and reconcile case report forms with RedCap data once monthly.

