#### **14.3 When and How to Withdraw Subjects**

In this intention-to-treat analysis plan, all participants who fill out a baseline survey will be included in analyses. As above, withdrawal will be determined by study staff only in the event of medical complications or death.

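### Section 14.2's 2-month limit for seriously ill participants is shorter than the RCT survey interval and conflicts with the Section 9.6 rule that missed surveys do not end follow-up

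*Combined protocol and SAP*

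**What the plan says.** Section 14.2 (Early Withdrawal of Subjects) sets two rules. For participants who cannot take part because of illness: "In the event of serious medical complications (or death) precluding participation, participants will be censored after 2 months of missing data". For everyone else: "In all other cases, staff will continue to request surveys until 2 months following the study endpoint", the endpoint being month 12 in the RCT and month 3 in the run-in. Section 14.3 then adds that "withdrawal will be determined by study staff only in the event of medical complications or death", referring back to the preceding text.

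Section 9.6 (text after Table 5) sets a general rule with no exception for illness: "Participants will remain eligible for subsequent survey completion and follow-up even if surveys are missing". On how long this lasts, it is equally plain: "the same procedures will be conducted for each survey due-date until the 12-month follow-up point". It also provides for the very ill. Staff offer an interview, then an abbreviated survey and, at follow-up time points, a parent proxy report "in cases where participants are too ill to provide self report in writing or interviews". Reminders are sent "within a 28 day window before and after surveys are due". Section 13.5.1 adds an interview or a shortened survey "with only the PedsQL for those who do not complete all assessments or who request to drop out or who are too ill" to finish.

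The same part of Section 9.6 places RCT surveys at baseline, week 12 and months 6, 9 and 12.

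**The concern.** The two sections give site staff different instructions for the same person. Section 9.6 has them approach an AYA who missed week 12 through illness again at month 6. Section 14.2 appears to have them stop after 2 months, since it contrasts the censored group with those from whom surveys continue to be requested. Its place under early withdrawal, and the link in Section 14.3 to withdrawal determined by staff, point the same way. Section 14.4 speaks only of retaining baseline data and provides no further follow-up.

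A 2-month limit also sits badly with surveys about 3 months apart, because a single miss can use it up before the participant has had a full second opportunity. Someone who recovers enough to answer, or whose parent could answer, would not be asked. The group stopped would be the sickest survivors, in a trial whose outcome is quality of life, so the missingness would plausibly be related to the outcome. Section 2.1.2.6 reports that loss among surviving pilot participants (25% and 14% by arm) came mainly from medical complications.

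**Working it through.** The plan gives no calculation for this limit, so there is no figure to reproduce. The check is calendar arithmetic.

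**Inputs**
- Survey times: week 12 and months 6, 9 and 12 (Section 9.6). The primary time point is also described as 3 months (Section 1.2.2.1), so both day 84 and day 91.3 are used.
- Window: 28 days either side of the due date (Section 9.6).
- Limit: 2 months (Section 14.2).
- Conversion (assumption): 1 month = 365.25/12 = 30.44 days, so 2 months = 60.9 days.

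**Survey gaps.** With week 12 at day 84, the gaps are 84, 99, 91 and 91 days (2.8 to 3.2 months). All exceed 2 months.

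**Formulas.** Let D be the due day of the missed survey and N the due day of the next.
- Due-date clock: limit = D + 60.9, compared with the next window opening at N − 28.
- Window-close clock: limit = D + 28 + 60.9, compared with N − 28 and with N.

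| First miss | D | N − 28 | N | Due-date limit | Days before next window opens | Window-close limit | Days next window already open | Days before next due date |
|---|---|---|---|---|---|---|---|---|
| Week 12 (day 84) | 84 | 154.6 | 182.6 | 144.9 | 9.8 | 172.9 | 18.2 | 9.8 |
| Week 12 (as 3 months) | 91.3 | 154.6 | 182.6 | 152.2 | 2.4 | 180.2 | 25.6 | 2.4 |
| Month 6 | 182.6 | 245.9 | 273.9 | 243.5 | 2.4 | 271.5 | 25.6 | 2.4 |
| Month 9 | 273.9 | 337.2 | 365.2 | 334.8 | 2.4 | 362.8 | 25.6 | 2.4 |

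Differences were taken before rounding. With week 12 at day 84, the ordering is unchanged when 2 months is taken as 56, 60 or 62 days.

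**Surveys no longer requested, per affected living participant.** On the due-date clock: 3 after a first miss at week 12 (months 6, 9 and 12), 2 after a first miss at month 6, and 1 after a first miss at month 9. On the window-close clock, each count may be one lower, because the next survey may already have been sent.

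**End of final requests.** Section 9.6 gives 365.2 + 28 = day 393.2. Section 14.2 gives 365.2 + 60.9 = day 426.1. The two differ by 32.9 days.

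**The case against.** The strongest reply is that Section 14.2 is a deliberate exception. It applies only where complications preclude participation, and someone who can manage an interview, a short form or a proxy report is arguably not precluded. Sparing the families of gravely ill patients is a defensible aim. This stands in part: it narrows the group. But Section 9.6 carries no matching exception, Section 14.2 does not require those routes to have failed first, and a proxy may be unavailable because parent participation is optional (note to Section 3.2.1).

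Second, *censored* may be only an analysis label, in which case no contact is lost. That cannot be excluded. Nor does the text say which data must be missing. Chart data are abstracted monthly to month 3 and again at months 6, 9 and 12 (Section 9.5.1), without the participant having to respond. The surveys are the more natural reading, but this is not stated.

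Third, Section 4.1 allows for 26% attrition from medical complications, and Section 11.5.3.6 plans imputation, weighting and sensitivity analyses. These lessen the bias but do not replace answers that could have been collected. The pilot attrition figures also do not show that those lost would later have been able to respond.

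A reader might infer that the month-3 primary endpoint is at risk, because a clock started at the baseline survey or at illness onset could expire before week 12. The documents do not support this. The limit counts missing data, not time ill, and the text of Section 9.6 shows no RCT survey due between baseline and week 12. The HRV schedule labels 1 month a survey time point, but Figure 3B is not available to check. Even if a survey was due then, a miss would reach the limit on the due-date clock at 30.4 + 60.9 = day 91.3, inside the week-12 window (days 56 to 112).

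**Conclusion.** The conflict is real and the point is minor. On either clock that starts from a missed survey, the 2-month limit runs out before the next survey is due. On the due-date clock it runs out before the next window opens. If *censored* means that requests stop, a living participant can lose up to three later surveys on the due-date clock, and possibly fewer on the window-close clock.

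The effect falls on the exploratory month 6, 9 and 12 outcomes (Sections 1.2.3.6, 8.1.2.3 and 11.5.3.3). It should not be read as a threat to the primary endpoint or to the intention-to-treat set, since Section 14.3 keeps everyone with a baseline survey in the analyses. The number of participants affected, the surveys lost in total and the size of any bias cannot be computed from the documents.

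The conclusion assumes that the missing data meant are survey data, that the clock starts at the missed due date or at window close, and that censoring ends contact. Section 14.2 states none of these.

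**What to change.** Reconcile Sections 9.6, 14.2 and 14.3. For the RCT, state that:
- living AYA participants who have not withdrawn consent are offered each remaining scheduled survey through the Section 9.6 options, regardless of earlier misses or medical complications, and families may decline contact;
- AYA follow-up ends at death, with the date recorded, or at withdrawal of consent;
- medical complications alone do not end survey follow-up (amend the last sentence of Section 14.3 to match).

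Write the run-in rule separately, because Section 9.3.1 does not offer parent proxy there. State separately whether parent surveys continue after an AYA's death. Choose one end for final-survey requests: 28 days (Section 9.6) or 2 months (Section 14.2).

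If a limit on contact is intended, define *censored*, the data that count as missing and the start of the clock. Require that the Section 9.6 options have first failed, allow re-entry after recovery, express the limit in missed surveys rather than months, and cross-refer to it in Sections 9.6 and 14.3.

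The cost is a protocol wording change, including a decision on bereaved parents, and a few extra contacts with very ill families. The survey procedures already exist in Section 9.6.

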#### **14.3 When and How to Withdraw Subjects**

In this intention-to-treat analysis plan, all participants who fill out a baseline survey will be included in analyses. As above, withdrawal will be determined by study staff only in the event of medical complications or death.

#### **14.4 Data Collection and Follow-up for Withdrawn Subjects**

Unless explicitly indicated by participants who withdraw their consent, baseline data for all eligible patients will be maintained and utilized in analyses.

### **15.0 Risks to Subjects**

The intervention (“Promoting Resilience in Stress Management”, PRISM) and our surveys may address sensitive matters in that it they patients to identify stressors and negative thoughts. Adolescent and young adult participants may be prompted to think about the threat to their life posed by their cancer/tumor. During the coming together session and/or while completing surveys, parents may be prompted to think about the threat to their child’s life by their cancer/tumor. The topics to be covered may provoke sadness, anxiety, depression, fear or doubt for AYAs and/or their parents. Any spouse, caregiver, significant other, caregiver, etc. who participates in the coming together session may be also prompted to think about the threat to the AYA’s life posed by their cancer/tumor and these topics may provoke sadness, anxiety, depression, fear or doubt for AYAs and/or their parents.

Administrators of the intervention will be trained to inform the patient’s primary social work and/or medical teams if the patient and/or parents/guardians/spouses/significant others endorse thoughts of self-harm or harm to others. As part of their informed consent process, participants will be made aware of this policy, as well as the fact that confidentiality may be broken in the case that providers see an immediate threat to the patient’s or another’s safety. Patients who participate in the optional HRV measurement component of the study may experience some mild physical discomfort or skin irritation associated with wearing the ECG monitor. The risk is minimal, as this process is identical to standard ECG measurements obtained for clinical purposes, of which all participants will have undergone. No significant physical risks are expected to arise from the study. The primary risk to participants will be concerns about confidentiality, and stress of discussing the topic of their or their child’s cancer/tumor experience. While the potential risks to participants are low, we will take steps to ensure that all potential risks are handled appropriately as described

below. Due to the nature of the PRISM intervention, all staff and participants will be unblinded from the time of randomization.

We recognize the unique risks of data collection for an AYA population. The major risk is compromise of personal data. Thus, confidentiality procedures for all data will be a priority for this study. All data will be maintained on secure computers or in locked offices at Seattle Children's Research Institute (data collection center). The study results will be kept for at least ten years or until final analyses are completed, whichever occurs last, in order to ensure data quality. The subject's consent to use or share PHI does not expire. Access to the building where the study data will be kept at Seattle Children's Research Institute is limited to authorized personnel. The Lead RA and other researchers involved in this project have years of experience and has received ongoing training at Seattle Children's Research Institute on confidentiality as well as HIPAA confidentiality standards. Our and other previous trials have kept their data at Seattle Children's Research Institute in the recent past, and the security and confidentiality of the data have never been compromised.

**15.1 Alternatives:** Patients may opt not to participate in the research. Their care will not be affected in any way should they decline participation.

## 16.0 Potential Benefits to Subjects

We hypothesize that patients who receive the intervention will have diminished psychological distress and greater quality of life. We also hypothesize that parents/caregivers/significant others/spouses will benefit similarly from their child's/partner's participation because prior experience in pediatric cancer studies suggests it is personally important for some patients and caregivers to share their perspectives, challenges and growth experienced during their cancer. However, there may be no direct benefit for participating in this study if our hypotheses are wrong. More broadly, information gained from this study may heighten the understanding of the AYA cancer and progressive/recurrent tumor experience and elucidate strategies that foster resilience and promote better quality of life in this group of high risk patients. These strategies could be extended to the care of other AYA patients facing non-cancer or tumor-related life-threatening illness. This research has the potential to contribute to the research base concerning the promotion of optimal quality of life and mental wellness for all AYA patients.

## 17.0 Vulnerable Populations

**17.1** This study includes the following vulnerable populations:

- A. Individuals who are not yet adults (children, teenagers): Pediatric patients with serious illness are at risk for poor outcomes and may benefit from resilience-enhancing interventions in the future. We justify the inclusion of children in this project because the implementation of those interventions requires feasibility information and patient feedback. This study will provide those crucial data. Patients enrolling in this study may, in fact, benefit from the intervention; however, at the time of consent, we will ensure that all patients and families understand the objective of this study are to test the feasibility of this intervention such that it may be used prospectively in the future (see risks/benefits above).
- B. Pregnant women: There is a chance that a parent or spouse/significant other of a patient participant is pregnant and therefore could participate in the survey and/or 'coming together' portion of this study. This study does not involve interventions/invasive procedures to the woman or fetus and does not involve fetuses or neonates as subjects.

**17.2** This study will not include:

- 17.2.1** Prisoners
- 17.2.2** Cognitively impaired adults
- 17.2.3** Wards of state

## **18.0 Community-Based Participatory Research**

N/A

## **19.0 Sharing of Results with Subjects**

**19.1** Following completion of the study, a written summary of the main results will be provided to all interested participants.

## **20.0 Setting**

**20.1** Patients will be identified and recruited at their home institution (SCH, BCM, UPMC, CHLA). See section 23 for specifics.

**20.2** Study visits may be done in person at the hospital/clinic, in the inpatient room or in the outpatient clinical research center. PRISM sessions may also be conducted by phone or other web based communication (Zoom, WebEx, or Skype).

**20.3** There will not be an involvement of any community advisory board.

**20.4** All local research will be conducted via patients' home institution (i.e., in Seattle, research activities will occur within Seattle Children's Hospital and Clinics; however as above, patients/families may be at home and participate remotely via video call.)

## **21.0 Resources Available**

**21.1 Interventionist Training and Fidelity.** PRISM has been standardized through the creation of comprehensive protocols for those who implement it. Session-by-Session details are provided in the PRISM manual and in the Voicing My Choices Session Appendix document; an outline of each main section is listed in **Table 1**. All interventionists undergo at least 4 hours of training including role-playing and progressive mastery of intervention materials. The fidelity of all sessions will be systematically assessed via audio-recording. As possible, the PI or supervising team member will review the first 6 sessions for each interventionist, and score them for fidelity using a standardized tool (see appendix.) Intervenors will receive feedback regarding adherence to protocol and approach will be refined with additional training, if needed.

**21.2** Refer to **Table 3** for annual numbers of AYAs. We will consecutively enroll patients at SCH, BCM, UPMC, and CHLA.

**21.3** Refer to 'Table 4' for the Timeline of conducting and completing the research.

**21.4** The local research teams will work closely with the Hematology/Oncology medical and social work teams if outside resources or needs arise.

## **22.0 Prior Approvals**

**22.1** N/H R01 CA222486-01A1 was reviewed by the relevant study section. The final notice of award was received 8/1/13.

## 23.0 Participant Incentives

For the Run-In, participants will receive \$20 for each survey (total \$60 for 3 surveys) following the completion of each survey. No parent incentives or compensation will be offered as parents are not participants in the run in study.

For the RCT, all active patient participants will receive \$50 in total, in multiple installments. The total amount of \$50 will either be administered in two installment payments in the form of a \$25 gift card or five installment payments in the form of a \$10 gift card during the 12-month duration of the study. For example, for participants who are very ill or for whom survival is unlikely, we would provide the payment installments at earlier time points (e.g., baseline survey, 3-month survey). Per HRP-316: a) credit for payment will accrue as the study progresses as all participants will be paid in separate installments in conjunction with completion of a survey, b) payment will not be contingent on completing study procedures as the first payment installment would occur prior to the final study component (12-month survey). C) The amount of payment and the proposed method and timing of disbursement is neither coercive nor presented undue influence.

Participants will also receive small, non-monetary items, such as pens, lanyards, or tote bags throughout the study. Parents and guardians will also be offered non-monetary items such as pens, bags, stress balls, mugs, etc. Patients will receive payment regardless of if they complete the full RPCA, aRPCA, or the primary outcome measure only. Patients will not be paid more for participation in the optional HRV procedures.

Patient participants who complete both the baseline and 6-month surveys will also be entered in a raffle to win an iPad. At each site, raffles will take place once per year or after 10 participants have completed all study procedures, whichever occurs first. Each participant in the raffle will therefore have 10% or greater chance of winning an iPad.

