## **4.0 Study-Wide Number of Subjects**

### **4.1 Number of subjects:**

*Run-In PRISM-AC development, feasibility, and acceptability testing:* We will enroll up to 30 AYAs on a “run-in” pilot trial to refine process measures in conducting the newly added 5th session that is part of PRISM-AC. This phase of the study will be conducted ONLY at Seattle Children’s Hospital. Briefly, this “run-in” is designed as a cohort study to be conducted prior to launching the RCT phase of the study at Seattle Children’s and is expected to last approximately 6-12 months.

Parent/Caregivers/spouses/significant others may participate in PRISM session 6 (family meeting called “coming together”) but are otherwise not active study participants in this phase of investigation.

*RCT phase:* The target sample size is N=144 AYA participants (72/arm). Based on our prior work and characteristics of AYAs at participating centers (**Table 3**), we estimate identifying a total of 120 eligible AYAs/12-months (300 over the 30 months of enrollment). Assuming a conservative enrollment rate of 65% (versus 78% in phase II RCT), we expect to enroll and randomize 78 AYAs/12-months (target enrollment n=195 over the 30-months of recruitment). With a conservative attrition rate of 26% (due to medical complications as seen in pilot), we expect complete data collection on 144 AYAs (72/arm). This sample size achieves 80% power to detect an increase of 8.1 in mean Total PedsQL score, the main study outcome. Parent/Caregivers will also be invited to participate in this RCT phase of investigation as additional study subjects to complete surveys and participate in the PRISM session 6. Parents will complete surveys at the same time points as the AYAs. In our prior studies including AYA-parent dyads, >90% of caregivers participated. Hence, we expect complete data from a minimum of 128 caregivers (64/arm). Only one caregiver will be invited to complete questionnaires, and will be designated at enrollment.

**Table 3. Annual number of AYAs with advanced cancer (12-25 yrs-old) who are eligible, enrolled, and evaluable at 3 months for RCT**

Site	Total	Eligible	Enrolled	Evaluable
Seattle Children's	45	35	23	17
Texas Children's	55	35	21	16
Children's Hospital, Los Angeles	55	30	21	16
Children's Hospital, University Pittsburgh Medical Center	35	20	13	9
Total/12-months	190	120	78	58
Total for 30-month recruitment period:			195	144

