**Table 5. Resilience in Pediatric Cancer Assessment (RPCA) Instruments**

Objective	Concept	Instrument(s)	Source
Aim 1 (AYA Outcomes)	HRQOL (Primary Outcome)	PedsQL Generic Core and Cancer Modules (PedsQL) 20,21†‡	AYAs
	Anxiety/ Depression	Hospital Anxiety and Depression Scale (HADS) 22†‡	
	Symptom Burden	Memorial Symptom Assessment Scale (MSAS) 24†‡	
	Hope	Hope Scale 25†	
	Resilience	2-item Connor-Davidson Resilience Scale 	
		10-item Connor-Davidson Resilience Scale 94†	
Aim 2 (Parent Outcomes)	Anxiety	Generalized Anxiety Disorder Screener (GAD-7) 	Caregivers
	Depression	Patient Health Questionnaire (PHQ-8) 	
	HRQOL	Medical Outcomes Study Rand Short-Form 36 29‡	
	Family Experience	Family Experience Survey (HCAHPS) 	
Aim 3 (Activation)	Activation	Decision Making Involvement Scale 31‡	AYAs and Caregivers
		Survey of Caring for Children with Cancer (SCCC) †‡	
		Patient Activation Measure (PAM-13) 120†	
		Benefit Finding 121†	
	Demographic Questionnaire	Demographic information †	AYAs and Caregivers
	COVID-19 Impact	The COVID-19 Impact Questionnaire ‡	AYAs and Caregivers
	Quality of Care Checklist	Quality of Care Checklist †	AYAs

† Included in RPCA for “run-in”

‡ Included in abbreviated RPCA surveys

The full RPCA survey will be administered at baseline and week 12 in the RCT. (**Figure 3**). In order to optimize engagement, patients in both arms of the study will be asked to complete the abbreviated Resilience in Pediatric Cancer Assessment (aRPCA) during the

prospective longitudinal follow-up period (months 6, 9, and 12). The aRPCA will assess only selected outcomes (patient outcomes of HRQOL & symptoms, parent outcomes of HRQOL, and family activation variables), as described below. For those on the non-intervention arm of the study, staff will schedule a “study check-in” visit to coordinate the aRPCA completion and thank families for their continued participation.

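### The raffle rule in Section 23.0 does not guarantee the stated chance of at least 10%, because neither draw trigger caps the pool of entrants at ten

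*Combined protocol and SAP*

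**What the plan says.** The relevant text is in Section 23.0 (Participant Incentives) of the combined protocol and SAP.

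- Entry: "Patient participants who complete both the baseline and 6-month surveys will also be entered in a raffle to win an iPad".
- Draw: "At each site, raffles will take place once per year or after 10 participants have completed all study procedures, whichever occurs first".
- Conclusion: "Each participant in the raffle will therefore have 10% or greater chance of winning an iPad".

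The same section identifies the last procedure when it says that the first payment comes "prior to the final study component (12-month survey"). The text under Table 5 in Section 9.6 likewise describes a "prospective longitudinal follow-up period (months 6, 9, and 12").

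The section does not say who is in the pool at each draw beyond the entry rule. It is also silent on when the yearly clock starts, whether non-winners stay in for later draws, and how many iPads are drawn. The singular wording suggests one per draw.

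**The concern.** The conclusion is presented as following from the draw rule. It follows only if each draw has at most ten people in it. The count of ten in the rule is of people who have finished everything at month 12, whereas the people in the draw are those who have passed month 6. When the tenth participant finishes, the pool can also hold patients who are between months 6 and 12, and patients who completed month 6 but will never complete month 12. The yearly trigger is a time limit and puts no limit on numbers.

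At stake is whether a numerical statement about an incentive for seriously ill adolescents and young adults is true as written. Nothing in the trial's inference depends on it.

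**Working it through.** **Reproducing the stated figure.** Chance = prizes ÷ entrants in the draw. With one iPad and ten people, 1/10 = 10%. The floor therefore holds if every pool has ten people or fewer.

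**Logic, without retention assumptions.** Anyone who has completed all procedures has completed baseline and month 6, so completers are a subset of entrants. If the count trigger produces a site's first draw, the pool is at least 10 and the chance is at most 10%, the reverse of the stated bound. Over later count-triggered draws with a resetting pool, the average pool in steady state is about 10 × (share completing month 6) ÷ (share completing month 12). That is 10 at best. With 74% and 50% it is 10 × 0.74/0.50 = 14.8, a chance of 6.8%.

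**Inputs for the size.** Table 3 gives annual enrolment of 23 (Seattle), 21 (Texas), 21 (Los Angeles) and 13 (Pittsburgh), and recruitment lasts 30 months. Section 4.1 gives 26% attrition for the 3-month evaluable sample. Carrying 74% forward to months 6 and 12 is an assumption.

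**Expected pools at 74% retention.** Entrants per year e = 0.74 × annual enrolment. Months are counted from site opening.

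- First yearly draw at month 12: entries began at month 6, so the pool is e/2.
- Yearly draw over a full year of entries: the pool is e.
- Count trigger alone: the tenth completer arrives at month t = 12 + 12 × 10/e, and the pool is e × (t − 6)/12. For Seattle, t = 12 + 120/17.0 = 19.1 and the pool is 17.0 × 13.1/12 = 18.5.

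| Site | e | Month-12 draw | Full-year draw | Count trigger alone |
|---|---|---|---|---|
| Seattle | 17.0 | 8.5 → 11.8% | 17.0 → 5.9% | 18.5 → 5.4% |
| Texas, Los Angeles | 15.5 | 7.8 → 12.9% | 15.5 → 6.4% | 17.8 → 5.6% |
| Pittsburgh | 9.6 | 4.8 → 20.8% | 9.6 → 10.4% | 14.8 → 6.8% |

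The start of the yearly clock therefore matters. If it starts at site opening, the first draw comes early and the odds are above 10%. If it starts at the first entry (about month 6), the first draw at a larger site falls at about month 18, just before the tenth completer, with a full year of entries in the pool.

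**Simulation of the rule with both triggers.** Poisson accrual over 30 months; entry at +6 months and full completion at +12 months; draw at the earlier of 12 months or ten new completers since the last draw; one prize; pool resets. The (month 6, month 12) completion pairs were (74, 74), (74, 65), (74, 60), (74, 50) and (65, 50) per cent. Share of entrants with a chance below 10%:

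| Yearly clock starts at | Three larger sites | Smallest site |
|---|---|---|
| Site opening | about 45–70% | about 25–37% |
| First entry | about 68–84% | about 32–46% |

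If non-winners carry over and the chances are accumulated over draws, a wider grid (50–74% completing month 6, and 70–100% of those completing month 12) gives about 37–57% at the larger sites and 7–35% at the smallest.

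**The case against.** The strongest defence is that the sponsor meant each draw to be among the ten completers who trigger it. On that reading 1/10 = 10%, nobody falls below the floor, and the sentence is right; its use of a deduction suggests something of the kind was in mind. What stands is that the drafting may be loose rather than the arithmetic faulty. But that reading contradicts the entry rule, which admits patients at month 6 and would not exclude those who later miss month 12. The text needs correcting either way.

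Three stronger readings are tempting and are not supported.

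- A reader might infer that every draw waits for ten people to finish month 12. It does not. The yearly alternative brings some draws forward, and an early one can give odds well above 10%.
- A reader might infer that the larger sites cannot meet the figure. The documents show only that it is not guaranteed. The affected share rests on retention, clock start, carry-over and prize number, none of which they state. With 74% completing both time points and the clock at site opening, the median chance at the larger sites is 10%.
- A reader might infer that participants are promised these odds. The available text is protocol text. The consent pages are not in the material reviewed, so whether the figure reaches patients or parents cannot be seen.

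**Conclusion.** The concern holds in this form: under the entry and draw rules as written, a chance of at least 10% does not follow, because neither trigger caps the pool. That conclusion needs no assumption about retention.

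The size does. With one iPad per draw, a resetting pool, Table 3 accrual, 65–74% completing month 6 and 50–74% completing month 12, roughly 45–85% of entrants at the three larger sites and 25–45% at the smallest would have less than a 10% chance. The lower ends apply if the yearly clock starts at site opening, the upper ends if it starts at the first entry. These are projections, not facts in the documents.

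The point is minor. It bears on the accuracy of one incentive statement. The primary endpoint is at 3 months, before raffle entry, and sample size, power and analysis are untouched.

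**What to change.** Tie the draw to the pool it is drawn from. State in Section 23.0 that each site holds a draw one year after its last draw or as soon as ten participants have entered since that draw, whichever is sooner; that one iPad is drawn each time; that the tenth entry closes the pool; and that the pool then resets. State when the first yearly period begins. Every pool then has at most ten people, so the 10% floor is true by construction, and no entrant fell below it in any simulated scenario.

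The cost is a sentence or two and about 0 to 1 extra iPad per site over the trial. With the clock at site opening, average draws per site are 3.4–4.9, against 3.1–4.9 under the present rule. If the clock starts at the first entry and only 50% complete month 12, the average increase at the largest site is about 1.5 (4.7 against 3.2).

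If the present triggers are kept, delete the 10% figure, and check any participant-facing material for it. Do not replace it with a lower floor such as about 5%. With an uncapped pool no floor holds: simulated chances go down to about 3%, and at the larger sites up to about 6% of entrants (clock at opening) or 16–17% (clock at first entry) fall below 5%.
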